### Exclusion Criteria:

1. Patients with seizures secondary to metabolic, toxic, infectious or psychogenic disorder or drug abuse or current seizures related to an acute medical illness.
2. Presence of only non-motor partial seizures (without limb or facial movements, eye deviation or head turning)
3. Patients who require rescue medication during the Baseline Phase for more than 6 days.
4. Patients with any severe and/or uncontrolled medical conditions at randomization such as:
  - a. Liver disease such as cirrhosis, decompensated liver disease, and chronic hepatitis (i.e. quantifiable HBV-DNA and/or positive HbsAg, quantifiable HCV-RNA)
  - b. Uncontrolled diabetes as defined by fasting serum glucose > 1.5
  - c. Active (acute or chronic) or uncontrolled severe infections
  - d. Active, bleeding diathesis
5. Patients who have had a major surgery or significant traumatic injury within 4 weeks of study entry. Patients who have not recovered from the side effects of any major surgery (defined as requiring general anesthesia), or patients that may require major surgery during the course of the study.

PROPRIETARY MATERIALS OF THE HUGO W. MOSER RESEARCH INSTITUTE AT KENNEDY KRIEGER, INC. DO NOT USE OR DISCLOSE WITHOUT PERMISSION OF THE RESEARCH INSTITUTE

6. Patients who change the dose of the AEDs during 4 weeks before screening or during the baseline period.
7. Prior treatment with any investigational drug or use of any other cannabis product within the preceding 4 weeks prior to study entry.
8. Patients with a history of non-compliance to medical regimens or who are considered potentially unreliable or will not be able to complete the entire study. Those in foster care, unable to keep follow-up appointments, maintain close contact with Principal Investigator, or complete all necessary studies to maintain safety.
9. Pregnant or nursing (lactating) women, where pregnancy is defined as the state of a female after conception and until the termination of gestation, confirmed by a positive hCG laboratory test.

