### Laboratory tests and clinical procedures

- Weight, vitals and orthostatics will be monitored at baseline and at each visit. For subjects who are physically unable to complete standing orthostatics, only supine orthostatics will be collected. (Routine care)
- Neuroscores will be assigned at each visit by [name] as per her clinical routine. Neurologic exam and general physical exam will also be performed at each visit. (Routine care)
- Participants will be asked at each clinic visit about migraine frequency, severity (scale of 1-10) and duration, and any change in neurologic symptoms
- CBC, LFT, BUN, creatinine levels, electrolytes, will be measured at baseline, one month after baseline, one month and two months after maintenance dose steady state is reached, every 2-3 months during the Optimization Phase, and every three months (at each visit) during extension phase. Urine analysis will be performed at each of the extension phase visits (every three months).
- For subjects with a facial port-wine birthmark, frontal and profile photograph will be taken under standardized conditions with scoring of the port-wine birthmark for percent of face covered, thickness of birthmark, and darkness of birthmark color. Subjects without any facial port-wine birthmark will only need photographs taken at a single visit to confirm the lack of birthmark. (Research, See Study Visit Table)
- Concomitant AED plasma concentrations will be measured at baseline, one month after baseline, at steady state maintenance CBD dose, one month and two months after maintenance dose steady state is reached, every 2-3 months during the Optimization Phase, and at each extension phase visit.
- CBD plasma concentrations will be measured twice, at 6 and 10 weeks after baseline.
- hCG urine pregnancy test will be used for all female participants Tanner stage 2 and above (see Study Visit Table). We will tell subjects that they must be using effective birth control (for example, abstinence, birth control pills, contraceptive implants, condoms) and confirm that this is the case at each study visit. We will inform female subjects that they should not become pregnant or breastfeed a baby while on this study or for 30 days after taking Cannabidiol. We will also inform male subjects that they should not get their partners pregnant while on this study or for 30 days after taking Cannabidiol. Anyone who becomes pregnant while on the study will be removed immediately.

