## 2. Study Visits:

- Study Visit 1: Screening Visit: Informed consent process, eligibility criteria, provide seizure diary and instruct on use.
- Study Visit 2: Baseline Visit: Confirm eligibility and begin drug at dose 1 (see Visit Table and Dose Schedule). Provide study drug dosing record and instruct on use.

During the following Study Visits (see Visit Table), the participants will undergo clinical assessments, a neuroscore, have pictures taken, blood draws for laboratory tests, study drug accountability, concomitant medication survey, adverse event reporting, and study drug administration (see Visit Table for details).

An additional blood draw will also be necessary within 72 hours of a previous blood draw if the most recent result indicates a clinically significant ( $>3xULN$ ) elevation of ALT or AST. At minimum, the following tests should be repeated: ALT/AST, total bilirubin, and alkaline phosphatase. A GGT test will also be performed at that time. This bloodwork (ALT/AST, total bilirubin, and alkaline phosphatase and GGT test) will also be necessary if: 1) the dose of your study drug dose is increased after the escalation phase, 2) another drug which affects liver function is added, stopped, or has a dose change, or 3) you have one or more of the following symptoms without another explanation: fatigue, encephalopathy, nausea, vomiting, right upper quadrant pain or tenderness, abdominal pain or distension, fever, excessive bruising, excessive nose or gum bleeds, or petechia. All trial subjects with elevated LFTs will be followed closely until all abnormalities return to the baseline state as assessed by the investigator with  $AST/ALT < 3x ULN$  and will be followed until ALT/AST have normalized and symptoms resolve.

At the end of the Core Phase (Visit 10) and Optimization Phase (visit 14), participants will have the option between continuing in an extension study or weaning off of the study drug. Those who decide to continue will remain on the same dosage of medication and return for labs and clinical visits at least every three months or as deemed clinically necessary, and drug will be provided free of cost to the subject for at least one year, or until the drug is approved for clinical use for the treatment of epilepsy in patients with Sturge-Weber syndrome. Those who decide to wean off of the study will return for a final follow-up visit in 1 month (Week 52).

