**Treatment will continue until any of the following take place:**

1. Loss of seizure control defined as an increase of 50% in the average weekly number of seizures for a minimum of 4 weeks as compared to the average weekly number of partial-onset seizures during the 8 weeks baseline period. At this point, the subject's CBD dose can be decreased without requiring immediate withdrawal. The subject does not need to be withdrawn unless the seizure frequency does not drop below the 50% increase on the lowered dose.
2. Use of rescue medications longer than the maximum duration determined during the Baseline period.
3. Intolerable toxicity.
4. Treatment failure as defined above.
5. Pregnancy.
6. Withdrawal of consent.
7. Treatment duration completed as per protocol: completion of the Core phase (if patients do not accept to start the extension phase) or completion of the Extension phase.
8. Laboratory results indicate that the subject's liver function test (ALT or AST) has increased in any of the following ways:
  - >8xULN
  - >5xULN for more than 2 weeks
  - >3xULN **and** either (TBL >2xULN **or** INR >1.5)
  - >3xULN with the appearance of fatigue, nausea, vomiting, right upper quadrant pain or tenderness, fever, rash, and/or eosinophilia (>5%)

*g. Description of what happens to participants receiving therapy when study ends or if a participant's participation in the study ends prematurely.*

At study's end GW Pharmaceuticals will continue to provide drug to any patient doing well on Epidiolex and wanting to remain on it (extension study), at least until they have obtained an indication for pediatric epilepsy and it can be billed to the patient's insurance company. All others will be weaned off of the study drug over a month and seen back for one final follow-up visit one month later. For those discontinued specifically due to elevated liver function tests, they will continue to be followed until all abnormalities return to the baseline state as assessed by the investigator with AST or ALT <3xULN. Any patient removed early from the study, and all participants at the end of the study wishing to remain

**PROPRIETARY MATERIALS OF THE HUGO W. MOSER RESEARCH INSTITUTE AT KENNEDY KRIEGER, INC. DO NOT USE OR DISCLOSE WITHOUT PERMISSION OF THE RESEARCH INSTITUTE**

[name] patient will continue to be cared for by [name] and seen at the Hunter Nelson Sturge-Weber Center.

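### Entry and re-enrollment criteria set no ALT, AST or bilirubin limit, so drug can be started at liver values that the protocol itself treats as grounds to stop

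*Combined protocol and SAP*

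**What the plan says.** **Entry.** Section 5, exclusion 4 bars conditions that are severe, uncontrolled or both, with an open list of examples. The liver entry, 4a, is "Liver disease such as cirrhosis, decompensated liver disease, and chronic hepatitis", with hepatitis B and C markers. No enzyme or bilirubin value appears there or in inclusion items 1 to 5.

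**Timing.** Section 4a (Laboratory tests) states: "CBC, LFT, BUN, creatinine levels, electrolytes, will be measured at baseline, one month after baseline". Section 4b (Study Visits) states: "Study Visit 2: Baseline Visit: Confirm eligibility and begin drug at dose 1". No text requires the liver result to be seen before that dose.

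**Stopping.** Section 4f, item 8 ends treatment when ALT or AST "has increased in any of the following ways". Four limits follow, all stated as multiples of ULN.

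**Monitoring and recovery.** Section 4b requires a repeat draw within 72 hours when ALT or AST exceeds 3xULN. It adds that subjects with raised tests are followed to their baseline state with values below 3xULN, and "will be followed until ALT/AST have normalized and symptoms resolve". Section 4g repeats the target after a liver stop: "For those discontinued specifically due to elevated liver function tests, they will continue to be followed until all abnormalities return to the baseline state", again with a value below 3xULN.

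**Re-enrollment.** Under inclusion item 5, a subject who failed continuation criteria and withdrew may return under a new ID if the inclusion criteria are met. The PI and sponsor decide case by case, and the return can be no sooner than 4 weeks after the last follow-up visit.

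**The concern.** The protocol treats certain liver values as reasons to end drug but does not say that they bar starting it. Other stopping grounds do have an entry counterpart: pregnancy (exclusion 9) and rescue medication (exclusion 3). Diabetes even has a laboratory cut-off in exclusion 4b. The liver rule has none, which looks like an omission and not a choice.

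What is at stake is avoidable exposure of a subject with marked enzyme elevation. Subjects may be as young as 1 month and take 1 to 5 anti-epileptic drugs. Section 8b says the effects of CBD given with drugs cleared by the enzymes it inhibits are unknown. Tolerability is part of the primary objective in a study of 10. Section 7c stops enrollment after three removals for side effects or lack of benefit. If a pre-existing elevation led to a stop that was counted as a side effect, it would use one of those three.

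**Working it through.** The plan gives no figure to reproduce here. The check sets the stopping limits against the entry criteria.

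**Step 1. The four item 8 limits against entry.**

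| Limit (ALT or AST) | Met by one baseline enzyme value alone? | Stated at entry? | Closed by barring >3xULN? |
|---|---|---|---|
| >8xULN | Yes | No | Yes |
| ">5xULN for more than 2 weeks" | No, needs duration | No | Yes |
| >3xULN with total bilirubin >2xULN or INR >1.5 | No, needs bilirubin or INR | No | Yes |
| >3xULN with listed symptoms, rash or eosinophilia | No, needs those signs | No | Yes |

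Stated at entry: 0 of 4. Met by a single enzyme value: 1 of 4. Checkable from a single baseline draw: 2 of 4, if the planned liver panel includes bilirubin (assumed; Section 4a does not list its components). Closed by a bar at >3xULN: 4 of 4, because every limit needs ALT or AST above 3xULN (minimum thresholds 8, 5, 3 and 3).

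**Step 2. Worked cases, each in a subject whom the investigator does not exclude under item 4.**

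- ALT 9xULN: no written numeric limit is broken at entry, but 9 > 8, so the first stopping limit is exceeded.
- ALT 4xULN with bilirubin 2.5xULN: no written numeric limit is broken, but 4 > 3 and 2.5 > 2, so the third limit is met.
- ALT 4xULN alone: no stopping limit is met; only the 72-hour repeat applies. But returning to 4xULN does not satisfy <3xULN, so the two halves of the recovery target conflict.

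**Step 3. Two readings of item 8.** If the wording refers to the level, the first two subjects are started and must then stop. If it refers to a rise on treatment, a subject stable above a limit stays on drug under the repeat draw, follow-up and investigator judgement. Neither reading supplies an entry rule.

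**Step 4. Choice of bar.** An alternative is >5xULN, or >3xULN with bilirubin, INR or symptoms. It would still admit isolated values above 3 and up to 5xULN, the group in the third case. It would also need INR, which is not among the tests listed in Sections 4a and 4b. The plain >3xULN limit avoids both problems.

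**Step 5. Re-entry interval** (1 month taken as 30 days, and a new 8-week baseline assumed). Section 4g states: "All others will be weaned off of the study drug over a month and seen back for one final follow-up visit one month later". From the stop to re-enrollment: 30 (wean) + 30 (to final visit) + 28 (wait) = 88 days. To re-dosing: 88 + 56 = 144 days, or 144/30 = 4.8 months. From the last dose: 30 + 28 + 56 = 114 days. This interval is reassuring, but it is a time condition and not a laboratory one.

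**The case against.** The strongest reply is that the investigator can already act. Exclusion 4 covers uncontrolled as well as severe conditions, its list is open, and the values nearest an immediate stop are the ones most readily excluded by judgement. The subjects are known to the PI, who reviews all safety data. A baseline value above 3xULN triggers a repeat within 72 hours, and the first week's dose is only 2 mg/kg/day, so the likely worst case is brief, low-dose exposure. All of this stands and limits the harm. It does not close the gap, because the repeat draw and item 8 act only after dosing may have begun, and judgement cannot use a result that nobody is required to see first.

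It is also fair that a baseline liver test lets each subject's change be assessed, and that attribution is limited mainly by the uncontrolled design, which an entry limit would not cure. I therefore do not rest the point on attribution.

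A reader might infer that any raised baseline value already meets a stopping rule. It does not: only >8xULN is met by an enzyme value alone, and the symptom limit most naturally means symptoms that are new on treatment.

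A reader might also infer that a subject stopped for liver toxicity can simply be restarted. The documents do not support that. Follow-up runs to below 3xULN and to normalization, the PI and sponsor must agree, and re-dosing is nearly five months away. The last follow-up visit may reasonably be read as falling after recovery. What remains is that recovery is not written as a condition of re-entry.

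**Conclusion.** The point holds, and the change is worth making, chiefly for first entry. As written, the criteria allow a subject to be dosed with ALT or AST >8xULN, or >3xULN with bilirubin >2xULN. They also allow entry above 3xULN, where the recovery target cannot be met by returning to the entry value. The re-enrollment gap is real but secondary.

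The size is 0 of 4 stopping limits reflected at entry. The documents give no frequency of raised baseline enzymes, and with 10 subjects the number affected may be zero.

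The conclusion assumes that the investigator does not exclude the subject under item 4, and that the Visit Table does not schedule an earlier liver test with review before dosing. An earlier draw would ease the timing problem but would not by itself create an eligibility limit. It would be too strong to say that the protocol has no liver safeguard at entry, or that it will lead to such subjects being dosed.

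**What to change.** 1. Section 4b (Study Visits): require ALT, AST and bilirubin results to be reviewed before the first dose.
2. Section 5, exclusions: exclude or defer any subject with ALT or AST >3xULN. This one limit closes all four item 8 limits at entry, needs no INR, and agrees with the protocol's own recovery target (apart from a value of exactly 3xULN).
3. Section 5, inclusion item 5: state that all inclusion and exclusion criteria, including this limit, apply at re-enrollment, and that recovery under Sections 4b and 4g must be complete after any liver stop.

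The cost is protocol wording, an occasional deferred candidate, and possibly a blood draw a few days earlier, which may mean an extra trip or a local draw. No test is added if the planned liver panel includes bilirubin.

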#### 4. Study Procedures

a. *Study design, including the sequence and timing of study procedures (distinguish research procedures from those that are part of routine care).*

**Study Overview:** Investigator Initiated Expanded Access Study in 10 participants with Sturge-Weber syndrome brain involvement, medically refractory seizures and [name] participants at the Hunter Nelson Sturge-Weber Center at the Kennedy Krieger Institute

We hope to gain an understanding of the utility of pure CBD use for the treatment of drug resistant epilepsy in Sturge-Weber syndrome in this open-label dose-finding observational study. A baseline seizure frequency will be recorded for each subject in a diary for eight weeks prior to investigational drug initiation and parents/caregivers will document seizures on a daily basis throughout the study period (see seizure log). Investigational drug (CBD) will be administered as an adjunct to all current anti-epileptic drugs. All subjects will, at minimum, be clinically evaluated at screening, baseline, weekly for the first 6 weeks after drug initiation, then 4 weeks and 8 weeks later during the Core Phase. During the Optimization Phase they will be followed every 6-12 weeks (see Study Visits Table for precise timeline).

PROPRIETARY MATERIALS OF THE HUGO W. MOSER RESEARCH INSTITUTE AT KENNEDY KRIEGER, INC. DO NOT USE OR DISCLOSE WITHOUT PERMISSION OF THE RESEARCH INSTITUTE

**Method of administration:** Cannabidiol oral solution 100 mg/ml will be administered orally. The participants will be treated on an outpatient basis and will not require inpatient hospital admission.

**Dose / titration schedule:** Initiation of treatment will begin with 2 mg/kg/day given in two divided doses. The dose will be increased by 3 mg/kg/day after seven days and then by 5 mg/kg/day every seven days up to a maximum dose of 25 mg/kg/day given. The dosing schedule will be as follows, as tolerated:

- Start of study : 2 mg/kg/day; subject will be evaluated here
- Week 1: Increase dose by 3 mg/kg/day for total daily dose of 5 mg/kg/day; subject will be evaluated here
- Week 2: Increase dose by 5 mg/kg/day for total daily dose of 10 mg/kg/day; subject will be evaluated here
- Week 3: Increase dose by 5 mg/kg/day for total daily dose of 15 mg/kg/day; subject will be evaluated here
- Week 4: Increase dose by 5 mg/kg/day for total daily dose of 20 mg/kg/day; subject will be evaluated here

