#### **Measurement of changes in seizures (Routine)**

Change in seizure frequency is the primary outcome measure for this pilot trial. All seizure types will be classified before study entry. Seizure frequency for each seizure type will be recorded during a baseline of 8 weeks before administration of CBD. Seizure type, frequency will be monitored during baseline and treatment as recorded in a patient diary (see seizure log). For assessing the efficacy of CBD, the investigator will count the change in the frequency of seizures (i.e., tonic seizures, clonic seizures, tonic-clonic seizures lasting more than 3 seconds, focal motor seizures, focal seizures with impaired consciousness, atonic seizures, myoclonic seizures including myoclonic absences). In addition, parents/caregivers will report the following **secondary outcome measures**:

- Change in average seizure duration by seizure type
- Change in the number of episodes of status epilepticus, defined as convulsive seizure lasting longer than 10 minutes
- Change in the number of uses of rescue medication
- Change in the number of ER visits/ hospitalizations

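### The cannabis exclusion, tied to an undefined study entry, leaves at least the first 4 of the 8 baseline weeks uncovered, so the measured seizure change can be biased in either direction

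*Combined protocol and SAP*

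**What the plan says.** Section 5 of the protocol, Exclusion Criteria, item 7 excludes recent investigational drugs and "use of any other cannabis product within the preceding 4 weeks prior to study entry". Item 6, immediately before it, excludes "Patients who change the dose of the AEDs during 4 weeks before screening or during the baseline period".

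The baseline is defined twice in section 4a. The Study Overview states: "A baseline seizure frequency will be recorded for each subject in a diary for eight weeks prior to investigational drug initiation". The subsection on measuring seizures states: "Seizure frequency for each seizure type will be recorded during a baseline of 8 weeks before administration of CBD".

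The visit list in section 4b gives the timing. Visit 1 (Screening) is "Informed consent process, eligibility criteria, provide seizure diary and instruct on use". Visit 2 (Baseline) is "Confirm eligibility and begin drug at dose 1". The diary therefore starts at Visit 1, the drug starts at Visit 2, and the baseline lies between them.

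No section of the available text says which visit is study entry. The term recurs in exclusion item 5 and in section 4a ("All seizure types will be classified before study entry"), again without naming a visit.

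**The concern.** CBD-enriched cannabis contains the active ingredient under study. The Background (section 3) describes families of children with refractory epilepsy giving such products, with 16 of 19 parents reporting fewer seizures. An outside source of CBD during baseline is therefore a foreseeable way for the reference count to be disturbed, and item 7 shows that the plan regards prior use as a problem.

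Three things rest on that count:

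- the primary outcome, change in seizure frequency (sections 4a and 7a);
- the treatment-failure rule in section 4f, set at a 50% reduction, with a discretionary allowance to continue at 30%;
- the loss-of-control rule in section 4f, set at a 50% increase over the 8-week baseline.

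There are 10 participants and no control group, so an error in one subject's baseline is not offset elsewhere. Under section 7c, three removals for side effects or lack of benefit stop enrolment, and promising results would be used to size later studies.

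**Working it through.** The plan gives no sample size calculation or other figure to reproduce on this point. Two checks apply.

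**1. The 4-week window set against the 8-week baseline**

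| Reading of study entry | What item 7 covers | Baseline weeks left open |
|---|---|---|
| Visit 2 (drug start) | baseline weeks 5-8 | weeks 1-4 (4 of 8) |
| Visit 1 (screening) | the 4 weeks before baseline | weeks 1-8 (8 of 8) |
| Checked at both visits | the 4 weeks before screening and baseline weeks 5-8 | weeks 1-4 (4 of 8) |

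No reading covers the whole baseline. Item 6 does not close the gap, because it concerns changes of AED dose, and steady use of a cannabis product is not such a change.

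**2. What exposure would do to the recorded change**

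Inputs: f = share of the baseline exposed (0.5 or 1, from the table); r = seizure reduction produced by the outside product (assumed; 25%, 50% and 80% are cut-points used in the Background survey); T = true reduction on study CBD against a cannabis-free baseline (assumed 50%, the failure line).

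Recorded baseline as a fraction of the clean one: B = 1 - f × r. 
Recorded reduction: 1 - (1 - T)/B.

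With f = 0.5 and T = 50%:

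| r | B | Recorded reduction | True reduction needed to record 50% (1 - 0.5 × B) |
|---|---|---|---|
| 25% | 0.875 | 1 - 0.5/0.875 = 42.9% | 56.2% |
| 50% | 0.75 | 1 - 0.5/0.75 = 33.3% | 62.5% |
| 80% | 0.60 | 1 - 0.5/0.60 = 16.7% | 70.0% |

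All three fall below 50%. The first two stay above 30%; the third does not.

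With f = 1, the extreme under the Visit 1 reading, a true 50% reduction reads as 33.3% for r = 25% (B = 0.75) and as 0% for r = 50% (B = 0.5).

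The loss-of-control trigger moves too. With f = 0.5 and r = 50% it is met at 1.5 × 0.75 = 1.125, which is 12.5% above the drug-free rate.

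**The opposite direction.** Suppose that stopping cannabis raises seizures by w in 4 of the 8 weeks and that r = 0. Then B = 1 + 0.5 × w. For an assumed w of 25% to 100%, B runs from 1.125 to 1.5. A drug with no effect would show an apparent reduction of 1 - 1/1.125 = 11% to 1 - 1/1.5 = 33%.

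If use in weeks 1-4 is followed by a rise in weeks 5-8, B = 1 + (w - r)/2, so the net bias takes its sign from whichever is larger.

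**After the fix.** With f = 0 and no withdrawal inside the baseline, B = 1 and a true 50% reduction reads as 50%.

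**The case against.** The strongest reply is that this is a wording ambiguity with a narrow practical gap. Eligibility is assessed at Visit 1 and confirmed at Visit 2. If item 7 is applied both times, the only uncovered case is a family that is cannabis-free at screening, uses a product in weeks 1-4, and then stops. That is a natural reading, although the text does not compel it, and it still leaves half the baseline open. The Visit Table is not in the text available here and may fix the timing.

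A second reply is that the Background speaks of CBD-enriched cannabis as if it were one more AED, so that stopping it during baseline might count as a change under item 6. At most this reaches a change in use; steady use stays outside item 6.

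Four stronger readings are tempting, and the documents do not support them:

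- *That baselines are in fact contaminated.* Nothing says that any participant uses cannabis, and the survey in the Background lists no Sturge-Weber patients.
- *That the drug effect would always be understated.* Withdrawal could push the baseline up instead.
- *That misread responders would be removed.* Section 4f lets a subject continue at a 30% reduction if the drug is well tolerated, and lets the investigator weigh the overall reduction. A subject recorded at 33% meets the failure definition but could stay.
- *That the medication survey already captures the problem.* Section 4b lists it for visits after Visit 2, so as described it does not monitor use during baseline.

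The stated objective is tolerability and dose, with no hypothesis test. That limits the consequences, but seizure frequency is still the declared primary outcome.

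**Conclusion.** The concern holds as a gap between two adjacent criteria: baseline is protected against AED dose changes, but not in full against outside use of the study's own active ingredient. The gap is 4 of 8 baseline weeks under two readings of study entry and all 8 under the third.

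Its effect on results is conditional. For an exposed subject the recorded response could miss the truth by about 7 to 33 percentage points (50 - 42.9 to 50 - 16.7), given half the baseline exposed, an assumed product effect of 25% to 80%, and no rebound on stopping. A rebound would push the other way. How many of the 10 subjects are affected, possibly none, cannot be determined from the documents. This is a cheap improvement, not a flaw that invalidates the study.

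**What to change.** - Reword item 7 to use the same window as item 6: no investigational drug or other cannabis product in the 4 weeks before screening or at any time during the baseline period.
- Define study entry by visit, and apply the definition wherever the term appears (exclusion items 5 and 7, and the seizure-measurement subsection of section 4a).
- Ask explicitly about cannabis use since screening when eligibility is confirmed at Visit 2, and include it in the concomitant medication survey at later visits.
- If enrolment is complete, document each subject's cannabis use during baseline, and report the seizure result with and without exposed subjects.

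The drafting cost is one phrase, one definition and one question at a visit that already takes place. The recruitment cost depends on the current meaning. Under the Visit 2 reading, the cannabis-free period before drug start goes from 4 weeks to 4 + 8 = 12, so a family using cannabis would have to have stopped up to 8 weeks earlier, which may slow recruitment slightly. Under the Visit 1 reading they would stop no earlier than now.
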